Attachment 3: Sample Subject Symptom Card

CCI

1. INTRODUCTION

This is the Statistical Analysis Plan (SAP) applicable for the VAC18193RSV2002 trial. This SAP is applicable for the following analysis:

- **Primary analysis** will be performed when all subjects have completed the quarantine phase or discontinued earlier. The pre-challenge neutralization and pre-F ELISA, and post challenge RT-PCR, nasal mucous and tissue count, and clinical symptom data will be available although the analysis may be performed on snapshot data. All other data available at the time of primary analysis, including completed cellular data, will be included. Preliminary safety data, including Day 28 post-challenge, if available, will also be included.
- **Final analysis** will be performed when all subjects have completed the 6-month safety follow-up visit or discontinued earlier.

Depending on when the data are available, the primary and final analysis might be combined.

Additional interim analyses (blinded or unblinded) may be performed during the study for the purpose of informing future vaccine-related decisions in a timely manner, or upon health authority request.

This document contains all information needed for performing a full efficacy, safety and immunogenicity analysis. Which tables, listing and figures (TLF) need to be generated for each analysis will be described in separate data presentation specifications (DPS) documents.

1.1. Trial Objectives

Primary Objective

The primary objective is to assess a trend for the prophylactic efficacy of a single dose of 1×10^{11} vp of Ad26.RSV.preF administered intramuscularly to adults aged 18-50 years in the RSV challenge model in terms of reduction of nasal wash viral load as measured by the area under the curve (AUC) over time by quantitative reverse transcriptase-polymerase chain reaction (RT-PCR) compared to placebo.

Secondary Objectives

- To assess a trend for prophylactic efficacy of a single dose of Ad26.RSV.preF in the RSV challenge model in terms of reduction of nasal wash viral load as measured by the peak viral load of the RT-PCR compared to placebo.
- To assess the effect of a single dose of 1×10^{11} vp of Ad26.RSV.preF on viral load, as measured by RT-PCR and quantitative culture of RSV, and clinical symptoms on Day 6 and Day 7 post-challenge compared to placebo.
- To assess a trend for prophylactic efficacy of a single dose of 1×10^{11} vp of Ad26.RSV.preF in the RSV challenge model in terms of prevention of symptomatic RSV infection defined as two quantifiable RT-PCR measurements and one or more positive clinical symptoms of any grade from two different categories in the symptom scoring system (Upper Respiratory, Lower Respiratory, Systemic), or one Grade 2 symptom from any category compared to placebo.

- To assess a trend for prophylactic efficacy of a single dose of 1×10^{11} vp of Ad26.RSV.preF in the RSV challenge model in terms of prevention of symptomatic RSV infection defined as two quantifiable RT-PCR measurements and one or more positive clinical symptoms of any grade in any category from the symptom scoring system compared to placebo.
- To assess a trend for prophylactic efficacy of a single dose of 1×10^{11} vp of Ad26.RSV.preF in the RSV challenge model in terms of the weight of mucous secretions and tissue count over time compared to placebo.
- To assess the safety and tolerability of a single dose of 1×10^{11} vp of Ad26.RSV.preF administered intramuscularly.

Exploratory Objectives

- To assess a trend for prophylactic efficacy of a single dose of 1×10^{11} vp of Ad26.RSV.preF in the RSV challenge model in terms of clinical symptoms as measured by the AUC over time of symptoms collected by a graded symptom scoring system compared to placebo.
- To assess a trend for prophylactic efficacy of a single dose of 1×10^{11} vp of Ad26.RSV.preF in the RSV challenge model in terms of AUC for viral load (VL-AUC), as measured by quantitative culture of RSV from nasal wash samples, compared to placebo.
- To explore the relationship of humoral (including nasal wash samples if feasible) and cellular immunogenicity outcomes and the VL-AUC and the AUC for clinical symptoms.
- To assess a trend for prophylactic efficacy of a single dose of 1×10^{11} vp of Ad26.RSV.preF in the RSV challenge model in terms of prevention of symptomatic RSV infection defined as two quantifiable RT-PCR measurements and/or positive serological measurement of RSV infection in the context of immunization and pre-existing antibody and one or more positive clinical symptoms of any grade in any category compared to placebo.
- To assess a trend for prophylactic efficacy of a single dose of 1×10^{11} vp of Ad26.RSV.preF in the RSV challenge model in terms of respiratory parameters measured by spirometry during the study compared to placebo.
- To explore the relationships between clinical symptoms and viral load, as measured by RT-PCR and quantitative culture of RSV, in Ad26.RSV.preF subjects and placebo.
- To explore other immunologic parameters in relation to the VL-AUC by RT-PCR and AUC for clinical symptoms and occurrence of symptomatic RSV infection defined as two quantifiable RT-PCR measurements or more plus one clinical symptom of any grade.
- To explore the immune response of a single dose of 1×10^{11} vp of Ad26.RSV.preF compared to placebo.
- To explore humoral and cellular responses to challenge with RSV-A Memphis 37b in immunized and non-immunized subjects.
- To explore the relationship between immunogenicity and pre-existing Ad26 neutralizing antibody.
- To explore other potential efficacy endpoints, as defined in the statistical analysis plan (SAP), to determine the best efficacy endpoint to use in subsequent clinical studies investigating the vaccine's efficacy.

1.2. Trial Design

This is a single center, randomized, placebo-controlled, double-blind Phase 2a human challenge study, to be conducted in approximately 44 healthy male and female subjects aged 18-50 years who have been pre-screened for susceptibility to RSV infection, ie, have levels of RSV neutralizing antibodies compatible with susceptibility to RSV infection.

Subjects will receive single intramuscular doses of 1×10^{11} vp of Ad26.RSV.preF or placebo. More than 44 subjects will be vaccinated to account for withdrawals between vaccination and challenge. The challenge study site, hVIVO, has the capacity to challenge and house under isolation 22 subjects at a time and thus the study will be conducted in several cohorts with up to 22 subjects per cohort. Within each cohort, subjects will be randomized 1:1 to 1×10^{11} vp of Ad26.RSV.preF or placebo. A schematic overview of the study design and groups is depicted in [Table 1](#).

Table 1: Study Design

Group	N	Day -28	Day 0*
Group 1	22	Ad26.RSV.preF (1×10^{11} vp)	Challenge with RSV-A Memphis 37b**
Group 2	22	Placebo	

* ie, not less than 24 or more than 90 days after vaccination.

**Subjects will be challenged in two or more cohorts of up to 22 subjects per cohort. Within each cohort, subjects will be randomized 1:1 to 1×10^{11} vp of Ad26.RSV.preF or placebo.

Note: The infection rate (based on mucus weight, symptoms and viral shedding) in the placebo group will be followed on an ongoing basis by an unblinded individual who does not have any other study function to ensure a sufficient infection rate has occurred. If the infection rate is lower than anticipated, additional subjects may be enrolled, initially four additional subjects in each arm and up to 70 in total. This is to ensure that a high enough number of evaluable subjects is reached in each arm.

For further information related to the design of the study refer to CTP, Section 3.1.

1.3. Statistical Hypotheses for Trial Objectives

The primary hypothesis is that a single dose of 1×10^{11} vp of Ad26.RSV.preF shows a trend of reduction in VL-AUC of the quantitative RT-PCR in healthy subjects challenged intranasally with the RSV-A Memphis 37b virus, compared with healthy subjects given placebo who are similarly challenged. For further information refer to CTP, Section 2.2.

1.4. Sample Size Justification

A sample size of 44 challenged subjects (22 vaccinated and 22 placebo subjects) was chosen as this would provide sufficient evidence to assess if the challenge model is a reasonable approach to examine vaccine efficacy.

As this is an exploratory study, the statistical assumptions taken for the calculation of the sample size will need to be demonstrated to be correct for the analysis to be conducted as planned. For example, if the infection rate, from the study is considerably below 65% then the study will be considered to be underpowered to be able to accurately determine the stated aims. The 65% infection rate used for the sample size calculations is referring to 65% of the placebo subjects having detectable viral loads. The infection rate in the placebo group will be followed on an ongoing basis by an unblinded individual who does not have any other study function to ensure a

sufficient infection rate has occurred. More details regarding the infection rate monitoring are outlined in the monitoring plan. For further information related to the sample size justification of the study refer to CTP, Section 11.2.

1.5. Randomization and Blinding

Please refer to CTP, Section 5.

2. CHANGES TO PLANNED ANALYSES

The CTP states that only abnormality in ECG parameters will be listed. Moreover, all ECG parameters collected during the quarantine period will also be summarized in tables as described in the Section [7.4](#)

In addition, a sensitivity analysis of the primary endpoint is added. At the time of the final analysis the quantitative RT-PCR assay values under the lower limit of quantification (LLOQ) will be distinguished between ‘Detected’ (values between the lower limit of quantification and the limit of detection) and ‘Not detected’ (values below the limit of detection) values, and the primary end point will be recalculated as indicated in Section [6.1.1](#).

3. GENERAL ANALYSIS DEFINITIONS

3.1. Study phases

The baseline (or reference) value for safety and immunogenicity analysis will be defined as the value of the last available assessment prior to vaccination (Day -28). For ECG values the baseline (or reference) value will be defined as the value of the last available assessment prior to challenge on Day 0, since ECGs for safety assessment are performed only during the challenge period.

The baseline (or reference) value for the efficacy analysis will be defined as the value of the last available assessment prior to challenge on Day 0.

The safety analysis will present all results by period, based on the phase definition in Section [3.1.1](#).

The immunogenicity analysis will summarize all results in the following immunogenicity timepoints:

- Baseline (vaccination)
- 28 days post-vaccination*
- 28 days post-challenge

*Includes all assessments taken between 22 and 33 days after vaccination.

In case there are subjects for which samples were taken later than 33 days after vaccination, the results will appear in listings.

Moreover,

$$\text{Study Day} = \text{visit date} - \text{date of Vaccination}$$

Listings will be shown per phase and time point.

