4.1. Inclusion Criteria

- 1 Each subject must sign an ICF indicating that he or she understands the purpose of and procedures required for the study, is willing to participate in the study and attend all scheduled visits, is willing to be isolated and stay in the clinic for the quarantine phase, and is willing and able to comply with all study procedures and adhere to the prohibitions and restrictions specified in this protocol.
- 2 Subject is a man or woman, ≥ 18 to ≤ 50 years old on the day of ICF signature.
- 3 Subjects must be in good health, without significant medical illness, on the basis of a medical evaluation that reveals the absence of any clinically relevant abnormality and includes a physical examination (including height and weight), skin examination, medical history, vital signs (systolic and diastolic blood pressure and heart rate, respiratory rate, and body temperature), and the results of clinical laboratory tests performed within 56 days of vaccination. If there are abnormalities, the subject may be included only if the investigator judges the abnormalities or deviations from normal to be not clinically significant. This determination must be recorded in the subject's source documents and initialed by the investigator.
- 4 Subjects must have a non-clinically significant 12-lead ECG within 56 days of vaccination including:

- a) normal sinus rhythm (heart rate between 50 and 100 beats per minute [bpm], extremes included)
- b) QT interval corrected for heart rate according to Fridericia (QTcF) interval ≤ 450 ms
- c) QT interval corrected for heart rate according to Bazett (QTcB) interval ≤ 450 ms
- d) QRS interval < 120 ms
- e) PR interval ≤ 210 ms.

Note: Retesting of abnormal ECG values that may lead to exclusion will be allowed once without prior approval from the sponsor. Repeat ECG due to equipment failure will not count as a retest. Subjects with a normal value at retest may be included.

- 5 Subjects must be sero-suitable for RSV within 90 days of vaccination (low immunity to the RSV-A Memphis 37b virus using a virus neutralization assay).

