9.2.6.3. Electrocardiogram

Supine 12-lead ECGs will be performed within 56 days of vaccination and on Day –1 or Day –2 prior to challenge; ECGs will only be performed at other times during the study if clinically indicated based on signs and symptoms. ECGs will be interpreted locally.

For 30 minutes prior to the ECG, subjects should refrain from meals, hot or cold beverages and strenuous exercise, and should remain in a room with a comfortable temperature. Each ECG should be obtained after the subject has been at rest for at least 5 minutes.

Enrollment of a subject with abnormal ECG results is allowed as long as the investigator feels that these are not clinically significant and appropriate for the population.

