11.7. Safety Analyses

No formal statistical testing of safety data is planned. All safety data will be analyzed descriptively by regimen.

Adverse Events

The verbatim terms used in the eCRF by investigators to identify AEs will be coded using the Medical Dictionary for Regulatory Activities (MedDRA). All reported AEs with onset during the

active phases (ie, AEs emerging after vaccination up to 28 days post-vaccination or during the quarantine phase), and all SAEs, will be included in the analysis. For each AE, the percentage of subjects who experience at least one occurrence of the given event will be summarized by group separately for the vaccination phase and challenge phase.

Summaries, listings, datasets, or subject narratives may be provided, as appropriate, for those subjects who die, who discontinue study vaccine due to an AE, or who experience a severe AE or an SAE.

Summaries and/or listings may be provided separately for AEs with onset outside the active phases.

Solicited local (at injection site) and systemic AEs will be summarized descriptively. The overall frequencies per vaccine group as well as frequencies according to severity and duration will be calculated for solicited AEs. In addition, the number and percentages of subjects with at least one solicited local (at injection site) or systemic AE will be presented. Frequencies of unsolicited AEs, separately for all and vaccination-related only, will be presented by System Organ Class and preferred term. Unsolicited AEs will be presented separately for vaccination phase and quarantine phase.

Clinical Laboratory Tests

Laboratory abnormalities will be determined according to the FDA Guidance document (see [Attachment 1](#)), or in accordance with the normal ranges for the clinical laboratory parameter if no grades are available. If a laboratory value falls within the grading as specified in the FDA table, but also within the laboratory normal limits, the value is considered as normal. Emerging abnormalities will be tabulated.

Vital Signs

A tabulation of the distribution of temperatures per half-degree intervals will be provided. For systolic and diastolic blood pressures, heart rate and respiratory rate, the percentage of subjects with values beyond clinically relevant limits will be summarized.

Electrocardiogram

Any abnormalities in ECG parameters (at screening and on admission to the Unit) will be listed.

Physical Examination

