7.2. Clinical Laboratory Tests

For laboratory safety parameters, only abnormalities emerging will be tabulated by worst abnormality grade using the FDA table in [Attachment 1](#). Blood and urine for laboratory safety assessments will be collected within 56 days of vaccination, pre-vaccination, at 7 days post vaccination, prior to challenge on Day -1 or Day -2, post challenge at day 12 and Day 28. Moreover, blood for assessment of cardiac enzymes will also be collected on Days 3, 7, and 11.

An abnormality (toxicity grade or abnormality based on normal ranges) will be considered as emerging in a particular period if it is worse than the baseline value. If the baseline is missing, the abnormality is always considered emerging. A shift from ‘abnormally low’ at baseline to ‘abnormally high’ post baseline (or vice versa) is also emerging. In case a laboratory test result is censored (no numeric value is available, but only a verbatim term) then a numeric value will be imputed by a value exceeding the cut-off value with one unit. (<x: subtract 1 unit from x, >x: add 1 unit to x; <3.45 is imputed with 3.44).

In case no toxicity grades are defined for a test, the abnormalities (above/below normal range) will be used. In determining toxicity grades, the following rules are applied:

- worst grades/abnormalities are determined over the whole observational period for each trial period separately, including all post-baseline measurements of that period.
- The abnormalities ‘abnormally low’ and ‘abnormally high’ are considered equally important, i.e. if a subject has as well an abnormally low as an abnormally high value post-baseline, both abnormalities are shown in the tables. (This means that the sum of the percentages can be more than 100%)
- Note: as the grading scale for some parameters in the grading table has some gaps (zones where no toxicity grade definition exists), laboratory results falling in these zones will be allocated to the adjacent worst-case grade.
- If a laboratory value falls within the grading as specified in the grading table but also within the local lab normal limits, the value is considered as normal.
- HGB: for hemoglobin grades are based on both actual values and changes. Those grading will be listed separately. In addition, for the grading on the changes of HGB, the corresponding actual value should be at least grade 1.

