7.4. Electrocardiograms

ECGs will be carried on Days -2 or -1, 3, 7 and 11 for safety assessment.

The following measurements will be analysed:

- HR (bpm)
- PR (ms)
- QRS (ms)
- Uncorrected QT (ms)

QT values will be corrected for RR, even if provided in the DB. The following QT correction methods will be used (rounded to the integer value):

$$QT_{cB}(ms) = QT(ms) \times \sqrt{\frac{1000}{RR(ms)}} : \text{Bazett's square - root corrected QT}$$

$$QT_{cF}(ms) = QT(ms) \times \sqrt[3]{\frac{1000}{RR(ms)}} : \text{Fridericia's cube - root corrected QT}$$

If RR is missing, but HR is available from the same ECG reading, the following replacement will be made in the above formulas.

$$\frac{1000}{RR(ms)} = \frac{HR(bpm)}{60}$$

If HR is missing, it will be calculated using RR (if available) and rounded to the integer value (see formula above). HR from the vital signs section (i.e. pulse) will not be used in this ECG analysis section.

Any rounding will be performed after computation of the applicable parameters, and before any further handling.

Abnormalities for the Actual Values

The actual values for HR, PR, QRS and QTc will be categorized into abnormalities using the boundaries defined in the following table (Limits in this table overrule those presented in the protocol.):

Abnormality Codes	HR	PR	QRS	QTcorrected
“abnormally low”		NAP	NAP	
“abnormally high”		≥ 210 bpm	≥ 120 ms	
“abnormally low Grade 1”	[50-54]			
“abnormally low Grade 2”	[45-49]			
“abnormally low Grade 3”	<45 bpm			
“abnormally high Grade 1”	[101,115]			
“abnormally high Grade 2”	[116,130]			
“abnormally high Grade 3”	>130			
“]450 ms, 480 ms]”				$450 \text{ ms} < QTc \leq 480$ ms
“]480 ms, 500 ms]”				$480 \text{ ms} < QTc \leq 500$ ms
“More than 500 ms”				$QTc > 500$ ms

- No abnormalities will be defined for actual uncorrected QT values.
- Uncorrected QT ≥ 500 ms will be flagged and only shown in listings.

Abnormalities on the Changes from Reference (QTc Parameters)

Abnormalities on the change from reference will only be defined for corrected QT, as follows:

1. < 30 ms
2. [30; 60] ms
3. > 60 ms

Only increases by ≥ 30 ms will be considered as abnormalities.

Note: The QTc definitions for abnormalities follow the ICH E14 guidance.

Parameters to Analyze

- actual values: HR, PR, QRS, QT and QTc
- abnormality classifications for the actual values: HR, PR, QRS, QTc
- abnormality classification for the increases from reference: QTc

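### The SAP's only ECG reference is taken after vaccination, so a change between vaccination and admission is not labelled emergent unless it worsens after challenge; post-challenge laboratory and vital-sign emergence has the converse fault

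*SAP*

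**What the plan says.** **ECG.** SAP 3.1 sets the general safety baseline at the last assessment before vaccination, then makes one exception: "For ECG values the baseline (or reference) value will be defined as the value of the last available assessment prior to challenge". The justification it offers for departing from its own general rule is brief: "since ECGs for safety assessment are performed only during the challenge period". SAP 7.4 states that "ECGs will be carried on Days -2 or -1, 3, 7 and 11 for safety assessment". It counts an abnormality in an actual value as emergent when it is worse than at reference, and takes QTc change from the same reference.

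The protocol has an earlier ECG. Inclusion criterion 4 (Protocol 4.1) reads "Subjects must have a non-clinically significant 12-lead ECG within 56 days of vaccination including" and goes on to limits for heart rate, QTcF, QTcB, QRS and PR. Protocol 9.2.6.3, which sits under Safety Evaluations, says "Supine 12-lead ECGs will be performed within 56 days of vaccination". Protocol 11.7 says "Any abnormalities in ECG parameters (at screening and on admission to the Unit) will be listed".

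**Laboratory and vital signs.** Under SAP 7.2 an abnormality "will be considered as emerging in a particular period if it is worse than the baseline value", and that baseline is the pre-vaccination one. If no baseline exists, SAP 7.2 treats every abnormality as emerging. SAP 7.3 handles vital signs similarly. Protocol 9.1.5.1 takes laboratory samples and vital signs at entry to the Unit. Protocol 9.2.6.2 schedules troponin T and creatine kinase with the ECGs, on admission and Days 3, 7 and 11.

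**The concern.** Twelve-lead ECGs are part of the secondary endpoint on safety and tolerability. The study has two exposures, vaccine and challenge virus, and each needs a reference taken just before it. The SAP gives each data type only one. For ECG the reference follows vaccination, so anything that appeared in between is absorbed into it. For laboratory tests and vital signs it precedes vaccination, so anything that appeared before inoculation can be carried into the challenge-period counts. The cardiac data show the conflict most clearly: ECGs and cardiac enzymes are taken together, yet are judged against different starting points. A reader of the emergent tables could miss a vaccination-period ECG change, or attribute a pre-existing enzyme elevation to the challenge.

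**Working it through.** **1. Does the stated reason hold?** Three places say otherwise.
- Protocol 4.1 requires a pre-vaccination ECG for entry.
- Protocol 9.2.6.3 and 11.7 treat that ECG as safety data, not only as an eligibility check.
- SAP Table 2 starts the Challenge phase at the date and time of challenge. The admission ECG therefore falls in the Post-Dose period, or in Follow-up Vaccination if later than day 32. The chosen reference itself lies outside the challenge period.

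**2. Length of the interval absorbed.** Challenge is 24 to 90 days after vaccination (target 28), and admission is 1 or 2 days earlier.
- Target: 28 - 2 = 26 to 28 - 1 = 27 days.
- Window: 24 - 2 = 22 to 90 - 1 = 89 days.

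**3. The emergent rule applied to example patterns.** Grades are given in the order screening, admission, Day 3, Day 7, Day 11. Emergent means that any later grade exceeds the reference grade.

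| Pattern | Admission as reference (SAP) | Screening as reference |
|---|---|---|
| New at admission, persists (0,1,1,1,1) | not emergent | emergent |
| New at admission, resolves (0,1,0,0,0) | not emergent | emergent |
| New at admission, worsens (0,1,2,1,1) | emergent | emergent |
| First seen on Day 3 (0,0,1,0,0) | emergent | emergent |
| Present throughout (1,1,1,1,1) | not emergent | not emergent |
| Present at screening, absent at admission, back on Day 7 (1,0,0,1,0) | emergent | not emergent |

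The first two rows are the gap. The last row shows why admission should remain the reference for the challenge question. Three scheduled ECGs follow the SAP's reference; four follow a screening reference. No scheduled ECG lies both after the SAP's reference and before challenge, so the count of emergent ECG abnormalities before challenge is zero in each arm by construction.

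**4. QTc change, with assumed values** of 400, 445, 445, 440 and 442 ms at the same five visits.
- From admission: max(445 - 445, 440 - 445, 442 - 445) = 0 ms.
- From screening: 445 - 400 = 45 ms, in the SAP's 30 to 60 ms category.

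No value exceeds 450 ms, so the actual-value classes would not flag this subject either.

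**5. What the actual-value classes already recover.** Entry requires QTcF and QTcB at most 450 ms, QRS below 120 ms, PR at most 210 ms and heart rate 50 to 100. SAP 7.4 flags QTc above 450, QRS of 120 or more, PR of 210 or more, and grades heart rate from 54 downwards and from 101 upwards. For a subject within the entry limits, a QTc or QRS flag at admission is therefore new, and so is a PR flag except at exactly 210. A heart rate of 50 to 54 is both eligible and Grade 1, so its newness cannot be read from the class.

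**6. Laboratory tests and vital signs.** Worst grades are determined separately for each period, always against the pre-vaccination value. An abnormality absent before vaccination, present at admission and still present at Day 12 is emerging in the period containing admission and again after challenge. For troponin T and creatine kinase no pre-vaccination sample is scheduled, so the missing-baseline rule makes every post-challenge abnormality emerging, even one unchanged since admission.

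**The case against.** The case for the SAP is substantial. The cardiac risk that the protocol names is myocarditis from the challenge virus (Protocol 1.3.4), and the admission ECG is the right reference for it. Screening ECGs may be historical, 56 to 3 days before vaccination, which puts them 3 + 22 = 25 to 56 + 89 = 145 days before admission. The protocol planned only a listing; SAP section 2 adds tables of all ECG parameters from quarantine. Those include admission, with abnormality classes that need no reference, and safety tables are by regimen. Clinically significant findings can also be reported as adverse events. A pre-vaccination laboratory baseline is a legitimate description of change since vaccination, applied alike to both arms, and no formal safety testing is planned.

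Most of this stands, and it rules out three stronger readings.
- A reader might infer that an ECG abnormality arising after vaccination can never be emergent. The documents do not support that: one first seen on Day 3, 7 or 11 counts, as does an admission finding that worsens.
- A reader might infer that the vaccine's effect on ECG is not estimated by arm. Admission values are summarised by randomised regimen, and that comparison is informative without a change score.
- A reader might take the zero count to cover all emergent ECG abnormalities. It applies only to those before challenge.

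The objection leaves untouched the inaccurate reason, the missing screening-to-admission change by arm, and the enzyme rule. It also does not help a subject barred from challenge by a clinically significant admission ECG (Protocol 4.3), who has no scheduled ECG after the reference and cannot enter the emergent table.

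**Conclusion.** The point holds in this limited form. The reason given for the ECG exception conflicts with Protocol 4.1, 9.2.6.3 and 11.7 and with SAP Table 2. An ECG abnormality or QTc increase arising over the 26 to 27 days (22 to 89 across the window) between vaccination and admission becomes the reference and is labelled emergent only if it worsens after challenge. What is mainly lost is the QTc change category, the newness of low heart-rate grades and the vaccination-period emergent label; new QTc, QRS and nearly all new PR flags can still be read from the admission table.

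The converse laboratory and vital-sign problem also holds and is sharpest for cardiac enzymes. How many subjects either problem would affect cannot be derived from the documents. The conclusion assumes that the scheduled ECGs are done and that enrolled subjects meet the entry limits; Protocol 9.2.6.3 allows abnormal ECGs judged not clinically significant, which weakens the second assumption slightly. The primary efficacy analysis is not touched. The SAP should be corrected because this is a planned safety endpoint and the data needed are already collected.

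**What to change.** **SAP 3.1 and 7.4.** Delete the statement that safety ECGs occur only in the challenge period. Use the last pre-vaccination ECG as reference for the admission ECG, and tabulate emergent abnormalities and QTc change for that comparison by arm. Keep the admission ECG as reference for Days 3, 7 and 11.

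**SAP 7.2 and 7.3.** For the Post-Challenge period, add emergence against the last value before inoculation, beside the existing definition. Use that reference for troponin T and creatine kinase, so that the missing-baseline rule no longer decides their classification.

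**Cost.** SAP wording and one or two extra descriptive tables; no new assessments. The limitation to state with the table is that the screening ECG may be up to 56 days before vaccination.

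While these sections are open, Protocol 9.2.6.3 should be reconciled with Protocol 9.1.5.3 and SAP 7.4: the first restricts ECGs after admission to those clinically indicated, and the other two schedule them on Days 3, 7 and 11.
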